1.2.1 Treatment Assignment

Since this is a single-arm study, all participants will be assigned to the same treatment and no randomization is performed.

1.2.2 Independent Review Facility

MRI scans will be reviewed by a central MRI core laboratory, which will perform the diagnostic reads and assessment of MRI outcome measures. MRI scans should preferably be transferred to the central MRI core laboratory electronically. Data transfer from individual study sites to the central MRI core laboratory may take up to 7-10 days, if not done electronically. Upon receipt of the MRI scans from the study sites, the central MRI core laboratory will provide the diagnostic reads. MRI results must be made available to investigators prior to next dosing or prior to the Week 104 visit (refer to the Protocol (version 3.0), Section 5.1.3 for additional details on MRI safety management).

MRI facility qualification and scan quality control will be performed by the central MRI core laboratory.

Additional instructions regarding the procedures for MRI scan acquisition and transmittal to the central reading facility can be found in the MRI Manual.

1.2.3 Data Monitoring

An Internal Monitoring Committee (IMC) will be employed to monitor and evaluate participant safety throughout the study.

The incidence, severity, and nature of adverse events (AEs), serious adverse events (SAEs), amyloid-related imaging abnormalities (ARIA) – edema/effusion (ARIA-E) and amyloid-related imaging abnormalities – hemosiderin deposition (ARIA-H), and laboratory abnormalities will be assessed on a regular basis by the Sponsor's IMC, as documented in the IMC Charter.

The Sponsor Safety Scientist and the Study Clinical Scientist will review the SAEs periodically and submit IND safety reports to the regulatory agencies, Institutional Review Boards / Independent Ethics Committees, and the IMC for any unexpected or serious events (as well as to the iDMC for GRADUATE I/II if deemed necessary). The main scope of the IMC is to review accumulating safety data for gantenerumab under the Q1W dosing regimen. Through summary and review of study data, the IMC will help the study Clinical Scientist minimize subject exposure to undue risk. Starting from 8 months after first-patient-in, the IMC will meet approximately every 3 to 6 months to review summaries of overall rates of death, ARIAs, AEs, and SAEs.

2. STATISTICAL HYPOTHESES

No statistical hypotheses will be tested in this study. All analyses are descriptive or purely exploratory.

3. SAMPLE SIZE DETERMINATION

Determination of sample size is relative to the sample of participants assessed by amyloid PET imaging using florbetaben. The sample size for this study is determined as the number of participants needed for the estimated change from baseline to Week 104 in amyloid PET load to fall into a 10 CL confidence interval (CI) around its true value. With a standard deviation of 25.67 CL (see below), 150 participants are required to fulfill this criterion. However, due to a lower than expected screen failure rate at the end of the enrollment period, a total of 192 participants have been enrolled.

The standard deviation of amyloid reduction was estimated using amyloid PET data from the ongoing Studies WN25203 (hereafter referred to as “SCarlet RoAD”) and WN28745 (hereafter referred to as “Marguerite RoAD”) open label extension (OLE) periods (based on a cutoff date of 14 October 2019), yielding a value of 25.67 CL.

Uncertainties of the parameters affecting the estimation (e.g., drop-out rate, study drug discontinuation rate, and standard deviation) were assumed to be equivalent to a decrease in sample size of up to around 35% and were corrected for accordingly. This drop-out rate is calculated based on Marguerite RoAD OLE at Week 104 that was ongoing at the time the study protocol was written. A sample size increase may be considered if factors external to the study would warrant a change to the sample size assumption.

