6. STATISTICAL CONSIDERATIONS AND ANALYSIS PLAN

6.1 DETERMINATION OF SAMPLE SIZE

Determination of sample size is relative to the sample of participants assessed by amyloid PET imaging using florbetaben. The sample size for this study is determined as the number of participants needed for the estimated change from baseline to Week 104 in amyloid PET load to fall into a 10 CL confidence interval around its true value. With a standard deviation of 25.67 CL (see below), 192 participants are sufficient to fulfill this criterion.

The standard deviation of amyloid reduction was estimated using amyloid PET data from the ongoing Studies WN25203 and WN28745 OLEs (based on a cutoff date of 14 October 2019), yielding a value of 25.67 CL.

Uncertainties of the parameters affecting the estimation (e.g., drop-out rate, study drug discontinuation rate, and standard deviation) were assumed to be equivalent to a decrease in sample size of up to around 35% and were corrected for accordingly. This drop-out rate is calculated based on the ongoing Study WN28745 OLE at Week 104. A sample size increase may be considered if factors external to the study would warrant a change to the sample size assumption.

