5.3.3 Main Analytical Approach for Primary Endpoint

Descriptive summary statistics for the brain amyloid CL load at baseline, Week 52 and Week 104 as well as the change from baseline to Week 52 and to Week 104 will be produced on both the ITT and Amyloid-PET-longitudinal analysis sets. Descriptive summaries of the primary endpoint will present the mean, standard deviation, median, and minimum and maximum.

A Mixed Model for Repeated Measures (MMRM) analysis will be used to estimate the mean change in CL from baseline to Week 52 and to Week 104 on the ITT analysis set. The model will include the change from baseline in CL as the dependent variable, while adjusting for visit (as categorical), apolipoprotein E allele $\epsilon 4$ (APOE $\epsilon 4$) status (as categorical; carrier vs non-carrier), baseline CL, and baseline CL-by-visit. Visit will be treated as the repeated variable within a participant. An unstructured variance-covariance matrix will be applied to model the within-participant errors; in the case of non-convergence, compound symmetry will be used, together with a robust estimator of standard error ("sandwich" estimator).

In line with the primary estimand definition, data acquired after the ICE "Substantial reduction in drug exposure due to the COVID-19 pandemic" (as defined above) or more than 56 days from date of last dose will be excluded from the analysis and treated as missing for the primary analysis purposes.

There will be no data imputation for missing data. However, the MMRM model provides unbiased estimates and valid inference in the presence of missing data, under the MAR (missing at random) assumption.

The least squares means at Week 52 and at Week 104 will be estimated and presented with a 95% CI.

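### Does the SAP's sample size of 150 miss its own 10 CL precision target, and does the protocol's 192 contradict it?

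*SAP*

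**What the plan says.** SAP section 3 asks for the estimated Week 104 change in "amyloid PET load to fall into a 10 CL confidence interval (CI) around its true value". The standard deviation comes from two open-label extensions, "yielding a value of 25.67 CL". It then states: "With a standard deviation of 25.67 CL (see below), 150 participants are required to fulfill this criterion". Uncertainty in drop-out, study drug discontinuation and the standard deviation together "were assumed to be equivalent to a decrease in sample size of up to around 35% and were corrected for accordingly", and the following sentence reads "This drop-out rate is calculated based on Marguerite RoAD OLE at Week 104". On the number recruited it says: "However, due to a lower than expected screen failure rate at the end of the enrollment period, a total of 192 participants have been enrolled". SAP 1.2 gives the plan in protocol Version 1 as about 150 and repeats the reason for the excess.

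Protocol 6.1 and the synopsis use the same criterion, standard deviation and loss allowance, but with another number: "With a standard deviation of 25.67 CL (see below), 192 participants are sufficient to fulfill this criterion". Their sample size text does not mention 150 or over-recruitment. Protocol 3.1.1 and 4.1 give 192 as the number already enrolled. SAP section 1 says its language supersedes the protocol.

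**The concern.** Three things catch the eye.

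- Putting 35% into the stated inputs does not return 150. It returns 157 or 160, so the figure called required seems to fail the criterion it is meant to satisfy.
- Two documents attach two different numbers to one criterion.
- The 35% is introduced as covering three sources of uncertainty and is then called a drop-out rate, which could mean that nothing was set aside for drug discontinuation or for a larger standard deviation.

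The trial tests no hypothesis (SAP section 2), so this precision statement is the whole justification of its size. A real error here would mean the main estimate was planned with less precision than claimed.

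**Working it through.** **Inputs**

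- SD of change: 25.67 CL (SAP 3).
- Precision: 10 CL, read as full width, so half-width 5 CL. The text does not say which.
- Confidence level: 95%. This is an assumption, since SAP 3 gives none. It is taken from SAP 5.3.3: "The least squares means at Week 52 and at Week 104 will be estimated and presented with a 95% CI".
- Loss: approximately 35% at most (SAP 3).

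**Evaluable number.** n = (z × SD / half-width)² = (1.96 × 25.67 / 5)² = 10.063² ≈ 101.3, so 102. Iterating with the t distribution gives 104.

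**The plan's 150.** Enrolled = evaluable / (1 − loss), rounded up:

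| Loss | From 102 (normal) | From 104 (t) |
|---|---|---|
| 30% | 146 | 149 |
| 31% | 148 | 151 |
| 32% | 150 | 153 |
| 33% | 153 | 156 |
| 34% | 155 | 158 |
| 35% | 157 | 160 |

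150 comes back exactly at 32% (102 / 0.68 = 150), but not at 35%. Other readings at 35% are further away:

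- Multiplying by 1.35: 138 (t: 141).
- 90% interval: 72 / 0.65, so 111.
- 99% interval: 175 / 0.65, so 270.
- 95% with half-width 10 CL: 26 / 0.65 = 40.

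A 95% interval of full width 10 CL is therefore the only reading tried that lands near 150.

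**Size of the miss at exactly 35%.** 150 × 0.65 = 97.5 evaluable. Width = 2 × 1.96 × 25.67 / √97.5 = 10.19 CL. With t and 97 participants it is 10.35 CL. The excess is 0.2 to 0.35 CL in total width, or 0.1 to 0.17 CL on each side.

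**The 192 enrolled.** 192 × 0.65 = 124.8 evaluable. Width = 2 × 1.96 × 25.67 / √124.8 = 9.01 CL, or about 9.1 CL with t. The largest loss that still meets the target is 1 − 102/192 = 46.9% (normal) or 1 − 104/192 = 45.8% (t).

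**Room for a larger SD.** At 35% loss, the largest SD that keeps the width at 10 CL is 5 × √124.8 / 1.96 = 28.5 CL with 192 enrolled, against a planning value of 25.67. With 150 enrolled it would have been 5 × √97.5 / 1.96 = 25.2 CL.

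**The case for a change.** The best case for a change runs as follows. A ceiling that was corrected for should be met at the ceiling; if 32% was used, the SAP should say 32%. The allowance may also be drop-out alone. If so, 150 had no reserve, because at 35% loss it tolerates an SD of only 25.2 CL. Drug discontinuation does cost data: scans more than 56 days after the last dose are dropped (SAP 5.1.1 and 5.3.3), so participants who stop treatment but return for assessments can still lose their Week 104 value. Someone reading protocol 6.1 alone would take 192 as the calculated size.

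The descriptive part of this stands. The confidence level, the meaning of 10 CL and the exact loss are not stated, the drop-out sentence sits awkwardly with the one before it, and the protocol does not say in its sample size text where 192 came from.

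The inference to a failed calculation does not stand. The loss is worded as an approximate upper figure and the planned size as approximate too, and a gap between 150 and 157–160 is of the order that such rounding produces. Drug discontinuation is named among the things the allowance covers. The numbers do not conflict either: the SAP calls 150 required, the protocol calls 192 sufficient, both can be true, and the SAP, which takes precedence, explains the difference.

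The check above is also only a single-mean formula. The planned MMRM adjusts for baseline CL and APOE ε4 status and uses Week 52 data from participants without a Week 104 scan. Both features tend to narrow the interval, though the documents do not allow that gain to be quantified.

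**Conclusion.** No change to the plan is needed. On a 95% interval of full width 10 CL with SD 25.67, 150 enrolled fits a loss of about 31–32%. At exactly 35% it would overshoot by 0.2 to 0.35 CL of width, against a predicted Week 104 reduction of about 67 CL (protocol 3.3.5). That margin lies within the rounding of the stated allowance.

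The question has also been overtaken by recruitment. With 192 enrolled the expected width at 35% loss is 9.0 to 9.1 CL, and the target holds up to about 46–47% loss, or at 35% loss up to an SD of 28.5 CL. All analyses are descriptive or exploratory, so no decision rule depends on the exact width. The interval reported will be the one the model yields, whatever the planning paragraph says.

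This rests on the 95% level and full-width reading, which are inferred, and on the planning SD applying to this trial. Fuller wording would help a reader retrace the calculation, but would alter no analysis, estimate or conclusion.

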4. ANALYSIS SETS

The following analysis sets are defined:

Analysis Set	Definition
Intent to treat (ITT)	All enrolled participants (i.e., who gave informed consent, did not fail screening, and had at least one Amyloid PET scan with a valid quantitative measurement performed with either florbetaben or flutemetamol), whether or not the participant received the assigned treatment.
Safety-evaluable (SE)	All participants enrolled who received at least one dose of study treatment, whether prematurely withdrawn from the study or not.
MRI safety-evaluable (M-SE)	All participants of the SE analysis set who had at least one post-baseline MRI assessment.
Amyloid-PET-longitudinal	All participants in the ITT analysis set with a valid post-baseline quantitative amyloid PET measurement performed with either florbetaben or flutemetamol.
MRI modified intent-to-treat (MRI-mITT)	All participants in the ITT analysis set who had at least one valid volumetric MRI quantitative measurement.
MRI-longitudinal	All participants in the MRI-mITT with at least one valid post-baseline volumetric MRI quantitative measurement.

Opportunity for home dosing safety-evaluable (OH-SE)	All participants of the SE analysis set who did not discontinue study drug before week 26.
Home dosing by study partner safety-evaluable (H-SE)	All participants of the SE analysis set who received at least one dose of study treatment administered at home by caregiver / study partner.

ITT = intent to treat; H-SE = safety-evaluable with home dosing by study partner; M-SE = safety-evaluable with post-baseline MRI; MRI = magnetic resonance imaging; MRI-mITT = modified intent-to-treat with at least one valid vMRI measurement; OH-SE = safety evaluable with opportunity for home dosing by study partner; SE = safety-evaluable;.

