- Evidence of AD pathological process, as confirmed by amyloid PET scan by qualitative read by the core/central PET laboratory
- Prodromal or mild symptomatology, as defined by a screening MMSE score ≥ 22 and CDR-GS of 0.5 or 1.0, as well as a CDR memory domain score ≥ 0.5
- If the participant is receiving symptomatic AD medications, a stable dosing regimen for at least 3 months prior to screening and until start of study treatment
- Agreement not to donate blood or blood products for transfusion for the duration of the study and for 1 year after final dose of study drug
- Agreement not to participate in other research studies for the duration of this trial, unless these are related Roche-sponsored non-interventional studies.
- For women of childbearing potential: agreement to remain abstinent (refrain from heterosexual intercourse) or use contraceptive methods that result in a failure rate

of < 1% per year during the treatment period and for at least 16 weeks after the final dose of study drug

A woman is considered to be of childbearing potential if she is postmenarchal, has not reached a postmenopausal state (≥ 12 continuous months of amenorrhea with no identified cause other than menopause), and is not permanently infertile due to surgery (i.e., removal of ovaries, fallopian tubes, and/or uterus) or another cause as determined by the investigator (e.g., Müllerian agenesis). The definition of childbearing potential may be adapted for alignment with local guidelines or regulations.

Examples of contraceptive methods with a failure rate of < 1% per year include bilateral tubal ligation, male sterilization, hormonal contraceptives that inhibit ovulation, hormone-releasing intrauterine devices, and copper intrauterine devices.

The reliability of sexual abstinence should be evaluated in relation to the duration of the clinical trial and the preferred and usual lifestyle of the participant. Periodic abstinence (e.g., calendar, ovulation, symptothermal, or postovulation methods) and withdrawal are not acceptable methods of contraception.

If required per local guidelines or regulations, locally recognized adequate methods of contraception and information about the reliability of abstinence will be described in the local Informed Consent Form.

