4.5.5 Positron Emission Tomography Scan

Two radioligands may be used in this study: florbetaben for participants at all sites (in exceptional circumstances, the use of flutemetamol may be acceptable at sites where florbetaben is not available, but only after prior written approval from the Sponsor).

Screening PET scans must not be acquired prior to the availability of potentially exclusionary screening results in order to minimize radiation burden to participants. To allow sufficient flexibility for scheduling of the screening PET scan, screening procedures (including central reading of the MRI scans) ideally should be completed within 2–3 weeks before the screening PET scan is required.

A positive PET scan using any amyloid tracer, acquired outside this study protocol is not permissible to confirm participant inclusion due to the longitudinal PET imaging requirements for all subjects enrolled in this study.

After obtaining the signed Informed Consent Form at the clinical study site, the following assessments and procedures will be performed for all participants during each amyloid PET scanning session:

- The responsible physician or his or her designee at the PET imaging center will confirm a participant's suitability for undergoing the PET imaging after a brief medical assessment, which may include weight. The PET scan should not be performed if the participant has an ongoing ARIA-E.
- For women of childbearing potential (including those who have had a tubal ligation), a urine pregnancy test will be conducted within 24 hours before the PET scan. The result must be negative for the participant to receive the amyloid tracer.
- The participant must void his or her bladder prior to scanning.
- Placement of an IV catheter into a forearm or antecubital vein for the injection of the investigational PET tracer must occur.
- A target dose of 300 [\pm 10%] MBq for florbetaben or 185 [\pm 10%] MBq for flutemetamol will be administered intravenously as a single slow bolus. The cannula

will be immediately flushed with up to 5–15 mL of saline solution. It is recognized that due to scheduling, transit, or manufacturing issues, from time to time, it is possible that an imaging center may be delivered a dose of amyloid radioligand that is less than the target dose. In these cases, participants may still be injected. However, if the dose is < 70% of the target dose, no injection should be performed and the participant should be rescheduled for imaging.

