5.1 GENERAL CONSIDERATION

In the following sections, for all continuous variables for which descriptive statistics are indicated, the following statistics will be reported: the number of observations, the mean, median, standard deviation, and minimum and maximum. The 25th and 75th percentiles (Q1 and Q3) will also be reported for selected tables. Descriptive summaries of discrete data will include frequencies expressed in terms of number and percentage of participants.

For safety endpoints, the baseline is defined as the last available assessment prior to first study drug intake. For all other assessments, the baseline is defined as the last available assessment before or on the day of first study drug intake, unless specified otherwise.

All PD analyses and all clinical efficacy analyses will be performed on the ITT analysis set, unless specified otherwise. Safety analyses will be performed on the SE analysis set, except for analyses of MRI findings which will be performed on the M-SE analysis set and analyses of home administrations by study partner that will be performed on the SE, OH-SE, or H-SE analysis sets, as appropriate.

All analyses will be purely descriptive or exploratory without any formal hypothesis testing. For exploratory tests, a two-sided significance level of 5% will be used.

In general, missing outcome data will not be replaced or imputed unless specified otherwise. Number and percentage of missing data points will be reported for each visit for key endpoints of interest.

In statistical models using change from baseline of a given outcome measure as the dependent variable, participants with missing baseline outcome measure will be

Gantenerumab—F. Hoffmann-La Roche Ltd

Statistical Analysis Plan: WN29722 (GRADUATION)

18

Clinical Study Report: gantenerumab - F. Hoffmann-La Roche Ltd

Protocol Number: WN29722

Report Number: 1117435

18

excluded from the analysis. There will be no imputation of baseline value for outcome measures.

The impact of the COVID-19 pandemic on the study and its conduct will be monitored and the overall impact will be assessed and described in the Clinical Study Report.

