5.2 PARTICIPANT DISPOSITION

The analysis of participant disposition will be based on the ITT analysis set. The number of enrolled participants will be tabulated by geographical region, country, and site.

The number of participants enrolled, treated with study drug, discontinued study drug, discontinued study, and completed study will be tabulated. Reasons for study drug discontinuations and for study discontinuations will be listed and summarized.

Major protocol deviations, including major deviations with regard to the inclusion and exclusion criteria, will be summarized. Separate tables will be provided for COVID-19-related major protocol deviations and reasons for COVID-19-related major protocol deviations.

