5.5.4.2 Plasma Biomarker Analyses

Exploratory fluid plasma biomarkers will be assessed at each visit for tau and amyloid pathology as well as neurodegeneration, including, but not limited to, the following:

- p-tau
- A β 1-42
- Neurofilament light chain (NFL)
- Glial fibrillary acidic protein (GFAP)

The plasma concentration of these biomarkers will be assessed. Analysis of plasma biomarkers will be based on the ITT analysis set. Biomarker data will be summarized for each assessment visit using descriptive statistics of absolute values as well as change from baseline values.

An MMRM analysis will be used to estimate the mean change from baseline to Week 104 (but also to Week 24, 36, 52, and 76) for each plasma biomarker. The model will include the change from baseline in the plasma biomarker as the dependent variable, while adjusting for visit (as categorical), APOE ϵ 4 status (as categorical; carrier vs non-carrier), baseline biomarker and baseline biomarker-by-visit. Visit will be treated as the repeated variable within a participant. An unstructured variance-covariance matrix will be applied to model the within-participant errors; in case of non-convergence, compound symmetry will be used, together with a robust estimator of standard error ("sandwich" estimator). The MMRM model will be based on log-transformed biomarker data.

There will be no data imputation for missing data. However, the MMRM provides unbiased estimates and valid inference in the presence of missing data, under the MAR (missing at random) assumption.

Other exploratory plasma biomarkers may be reported separately.

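### The ITT set requires a valid quantitative PET value that entry does not require, so an enrolled participant with an unquantifiable screening scan can be left out of analyses that need no PET

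*SAP*

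**What the plan says.** SAP section 4 defines ITT as all enrolled participants, dosed or not. It explains enrolled, in a clause introduced by i.e., as having given consent, not having failed screening, and having "had at least one Amyloid PET scan with a valid quantitative measurement performed with either florbetaben or flutemetamol". No visit is named, so one valid scan at any time, including screening, is enough.

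The entry criterion in Protocol 4.1.1 is "Evidence of AD pathological process, as confirmed by amyloid PET scan by qualitative read by the core/central PET laboratory". No quantitative value is required. Protocol 4.5.5 requires the qualifying scan to be a study scan: a scan "acquired outside this study protocol is not permissible to confirm participant inclusion".

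ITT, or a set built on it, is then named for much of the reporting:

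- SAP 5.1: "All PD analyses and all clinical efficacy analyses will be performed on the ITT analysis set, unless specified otherwise".
- SAP 5.2: "The analysis of participant disposition will be based on the ITT analysis set".
- SAP 5.5.4.2: "Analysis of plasma biomarkers will be based on the ITT analysis set".
- SAP 5.7.2 and 5.7.4: baseline characteristics and the COVID-19 summaries use ITT.
- SAP 5.5.4.1: volumetric MRI uses MRI-mITT, defined in section 4 as "All participants in the ITT analysis set who had at least one valid volumetric MRI quantitative measurement".

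Safety uses SE (enrolled and at least one dose). ARIA and other MRI safety findings use M-SE, which is built on SE.

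**The concern.** A set called ITT should be fixed by entry to the trial. Here it also depends on a technical result, the quantification of a scan, which can fail after a valid visual read and has no bearing on most of the analyses that use the set. Disposition is the clearest case: it should account for everyone enrolled, and under this definition it need not. Cognition, plasma and volumetric MRI could lose usable data for an unrelated reason.

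The open time frame adds a second problem. If the screening scan cannot be quantified, the participant enters ITT only by providing a valid later scan. Whether that happens depends partly on how long the participant stays.

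There is also an ambiguity of wording. The PET condition sits inside the SAP's explanation of enrolled, and SE starts from participants enrolled. Read literally, the condition could carry into the safety set, although Protocol 6.5 has no such condition and SAP section 1 says that the SAP's language takes precedence over the protocol.

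**Working it through.** The documents state no figure for participants without a valid quantitative scan, so there is nothing to reproduce. The check has two parts: a reading of the text, and an illustration of size under stated assumptions.

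**1. Who can be excluded**

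- Every participant should have an in-study screening scan (Protocol 4.5.5). If it can be quantified, the participant is in ITT whatever happens later.
- If it cannot, the next scheduled scan is Week 52 (Protocol Appendix 1, Table 2). An early-termination scan is taken only when six months or more have passed since the previous one and radiation limits allow (Appendix 1, Table 4, footnote m).
- A participant is therefore outside ITT only if the screening quantification fails and no later scan is valid. Those who leave the study before a second scan cannot qualify; those who stay can.

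**2. How many**

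Inputs: 192 enrolled (SAP 3). Assumptions, not in the documents: q, the share of scans that cannot be quantified, 1% to 10% and independent between visits; L, the share leaving with no second scan, 10% to 35%. The 35% borrows SAP 3's planning allowance, which combines drop-out, drug discontinuation and uncertainty in the SD, so it serves only as an upper end.

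Expected exclusions = 192 × [L·q + (1 − L)·q²]. The second term counts only one later scan for those who stay, so it slightly overstates their exclusion.

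| q | L = 10% | L = 35% |
|---|---|---|
| 1% | 192 × (0.0010 + 0.00009) = 0.2 | 192 × (0.0035 + 0.000065) = 0.7 |
| 2% | 192 × (0.0020 + 0.00036) = 0.5 | 192 × (0.0070 + 0.00026) = 1.4 |
| 5% | 192 × (0.0050 + 0.00225) = 1.4 | 192 × (0.0175 + 0.001625) = 3.7 |
| 10% | 192 × (0.0100 + 0.0090) = 3.6 | 192 × (0.0350 + 0.0065) = 8.0 |

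The share of leavers among those excluded is L/[L + (1 − L)·q]. It runs from 0.10/(0.10 + 0.09) = 53% to 0.35/(0.35 + 0.0065) = 98%, against 10% to 35% of those enrolled. The effect on the whole set is small. At q = 5% and L = 20%, leavers are 19.2% of ITT instead of 20.0%; at q = 10% and L = 35%, they are 32.9% instead of 35.0%.

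**3. Direction**

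Suppose the true discontinuation rate is 35% (0.35 × 192 = 67.2 participants) and 10 screening scans cannot be quantified; both are assumptions.

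- 35% of the 10 leave before a second scan, and everyone who stays later has a valid scan: (67.2 − 3.5)/(192 − 3.5) = 63.7/188.5 = 33.8%.
- Failure persists within a person, so all 10 are excluded, and 35% of them discontinue: 63.7/(192 − 10) = 63.7/182 = 35.0%, no change.
- Failure persists and none of the 10 discontinues: 67.2/182 = 36.9%.

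The reported rate can therefore be too low, right or too high, depending on facts the documents do not give.

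**The case against.** The strongest reply is that the problem may never arise. The screening scan is mandatory and done under the study because longitudinal PET is needed, and a single valid scan satisfies the definition. No document reports an enrolled participant without one. This stands: exclusion is a possibility, not a recorded fact.

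A reader might infer that early leavers in general are dropped from ITT. They are not, because an early leaver with a valid screening value stays in. Nor are those who stop drug necessarily lost: Protocol 4.6.5 and 4.7.1 ask them to return for the PD assessments, and ITT does not require an on-treatment scan. The participants at risk are mainly those who leave the study, or decline to return, after a failed screening quantification.

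SAP 5.7.1 names no analysis set and reports the number enrolled, the size of each set, and withdrawals from study and from treatment with reasons. A shortfall in ITT should therefore be visible. That limits the harm but does not put the missing participants back into the ITT tables, and the enrolled count there has the same ambiguity of definition.

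For cognition, SAP 5.5.2 speaks of all participants at each visit, which leaves room to read the ITT default in 5.1 as not applying. The carry-over into SE is a literal reading and may not be intended, since SE has no PET wording of its own and the SAP counts 192 enrolled without mentioning PET validity. Finally, this is a single-arm study with no hypothesis tests, so no randomized comparison is at stake.

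**Conclusion.** The definition is at fault; its practical effect is probably slight. SAP 4 makes ITT depend on a result that entry does not require, and applies that set to analyses that do not use it. Among participants whose screening scan cannot be quantified, inclusion can depend on staying long enough for another scan.

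The number affected is not given and may be zero. The illustrative 0.2 to 8 of 192 rests wholly on the assumed q and L and on independence between visits.

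Two stronger readings are tempting. One is that the rule always makes the reported discontinuation rate look better; the third calculation shows that it need not. The other is that MRI analyses as a whole are affected; this holds only for volumetric MRI, since ARIA and other MRI safety findings use M-SE. The PET MMRM is unaffected, because SAP 5.1 already excludes participants with no baseline value from change-from-baseline models.

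This is a minor point, worth correcting because the correction is nearly free.

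**What to change.** - Define ITT as all participants who consented and did not fail screening, with no PET condition. Use it for disposition, baseline characteristics, COVID-19 summaries, cognition and function, and plasma biomarkers, and build MRI-mITT on it.
- Keep the PET condition only in the PET-specific sets. For change from baseline, require a valid baseline and a valid post-baseline value; the present Amyloid-PET-longitudinal definition names only the post-baseline one.
- Define SE as all participants who received at least one dose, so that the explanation of enrolled cannot bring a PET condition into safety.

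The cost is SAP wording and one analysis-set flag. No new data are needed, and the PET MMRM estimate does not change. Denominators in the ITT tables, including those for missing-data percentages, would rise by the number of participants restored.
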